8.3 Efficacy

8.3.1 Efficacy assessments

Diagnosis at presentation according to WHO definition of AML will apply and be recorded in the eCRFs.

Response assessments (bone marrow aspirate (BMA)/bone marrow biopsies (BMB)), peripheral blood, hematology, transfusion independence, extramedullary disease assessments) will be performed locally, by the Investigator, according to the assessment schedule depicted in [Table 8-1](#) for assessment of disease.

Bone marrow assessments will be performed at screening and pre-dose on C2D1 and C5D1 and every 3 cycles D1 thereafter until confirmed CR, and then every 6 cycles thereafter until progression, start of a new anti-neoplastic treatment (including HSCT), death, lost to follow-up or withdrawal of consent.

Hematology assessments will be performed at screening, and pre-dose on D1 and D8 of each cycle, on Day 22 of Cycle 1 and Cycle 2, at the end of treatment visit and every 12 weeks for subjects who enter post-treatment follow-up. In the absence of blood count recovery at C2D1 and beyond, complete blood count can be collected weekly for up to 2 weeks. Complete blood count results used for the response assessment will be derived from the best accompanying

[REDACTED]

laboratory hematology result within the time window from 1 week before and up to 2 weeks after the bone marrow assessment used to support the efficacy response assessment. All components (eg, platelets, absolute neutrophils) should come from the same test.

Response evaluation will be based on the Investigator's assessment based on standardized criteria as proposed by the International Working Group (IWG) and European Leukemia Network (ELN) for AML (Cheson et al 2003, Döhner et al 2017) (see [Table 8-2](#)). Disease classification at baseline and evaluation of response during study treatment will rely on bone marrow and peripheral blood assessment, as well as on the presence or absence of extramedullary disease, and status of transfusion dependence. For disease characterization at baseline, the last assessment of bone marrow (within 28 days before study treatment starts) and peripheral blood counts (within 14 days before study treatment starts) at the screening visit should be used. In case of missing data for the full assessment required to qualify for a given response, the overall assessment "unknown" will be assigned unless disease progression was seen in at least one compartment (i.e. bone marrow or blood, or appearance of extramedullary disease).

Subjects can be assessed for disease response (bone marrow assessment, hematology, transfusion dependence, extramedullary disease assessment) at any time if clinically indicated, for example in case of suspicion of progression/relapse. Therefore more frequent efficacy assessments may be performed at the investigator's discretion and recorded as an unscheduled visit in the eCRFs. Clinical suspicion of disease progression at any time will require a disease evaluation promptly, rather than waiting for the next scheduled assessment. In case of an unscheduled or delayed disease evaluation of any reason, subsequent assessments should be performed according to the originally planned schedule.

More frequent efficacy assessments may be performed at the Investigator's discretion, if medically indicated, and recorded on the Unscheduled Visit CRFs. All assessments will be analyzed.

Table 8-2 Response classification in AML at a given evaluation time (based on IWG Cheson et al 2003, ELN 2017 Döhner et al 2017)

Response Category	Definition ¹
Complete Remission	
Bone marrow:
 
 • < 5% blasts • no blasts with Auer rods 
Peripheral blood:
 
 • neutrophils $\geq 1.0 \times 10^9/L$ • platelets $\geq 100 \times 10^9/L$ • no circulating blasts 
No evidence of extramedullary disease (such as CNS or soft tissue involvement).

Complete remission with incomplete hematologic recovery (CRi)	
Bone marrow:
 
 • < 5% blasts • no blasts with Auer rods 
Peripheral blood:
 
 • neutrophils $< 1.0 \times 10^9/L$ or platelets $< 100 \times 10^9/L$

Response Category	Definition ¹
	
 no circulating blasts 
No evidence of extramedullary disease (such as CNS or soft tissue involvement).

Morphologic leukemia free state (MLFS)	
Bone marrow
 
 < 5% blast no blasts with Auer rods 
No evidence of extramedullary disease (such as CNS or soft tissue involvement)

Partial Remission (PR)	
Bone marrow:
 
 < 5% blasts AND presence of blasts with Auer rods 
OR
 
 ≥ 50% decrease from baseline in blasts in bone marrow AND blast count in bone marrow is 5% to 25% 
Peripheral blood:
 
 neutrophils ≥ 1.0 x 10⁹/L platelets ≥ 100 x 10⁹/L no blasts
Progressive Disease (PD)	
Evidence for an increase in bone marrow blast percentage and/or increase of absolute blast counts in the blood
 
 >50% increase in marrow blasts from maximum remission or baseline ,whatever is lower (a minimum 15% point increase is required in cases with <30% blasts at baseline; or persistent marrow blast percentage of >70% over at least 3 mo; without at least a 100% improvement in ANC to an absolute level (>0.5 X 10⁹/L [500/µL], and/or platelet count to >50 X 10⁹/L [50 000/µL] nontransfused); or >50% increase in peripheral blasts (WBC X % blasts) to >5 X 10⁹/L (>25 000/ µL) (in the absence of differentiation syndrome); or New extramedullary disease
Stable disease	
Absence of CR, CRi, PR, MLFS, and criteria for PD or relapse are not met

Relapse from CR or CRi	
Only in patients with a CR or CRi. Any of the following:
 
 Reappearance of blasts in peripheral blood 
OR
 
 ≥ 5% blasts in bone marrow 
OR
 
 (Re-)appearance of extramedullary disease
Unknown	
In case the response assessment was not done or the assessment was incomplete

¹ If not defined otherwise, all of these criteria apply

Evaluation of transfusion dependency

RBC and platelet transfusions will be assessed at baseline as well as during the course of the trial for all patients. Transfusion of blood products will be recorded in a separate module of the CRF. The type of transfusion, start and end date as well as the volume of blood product will be captured at each visit with hematologic assessment. A period of at least 8 weeks without any transfusion has been taken as a convention to define the status of transfusion independence.

Transfusion dependence and independence for RBC and/or platelets are defined below:

Transfusions for intercurrent diseases or events not due to AML (e.g. bleeding due to trauma, surgical procedures) should not be taken into account for the following:

Transfusion independence:

- Before first day of study treatment (C1D1): subjects having received no RBC or platelet transfusions within the 8 consecutive weeks prior to enrollment/first day of study treatment (C1D1)
- On or after first day of study treatment (C1D1) : absence of any RBC or platelet transfusion during any consecutive 8 weeks

Transfusion dependence:

- Transfusion dependence at baseline is defined as at least one RBC or platelet transfusion in the 8 weeks prior to C1D1

Extramedullary disease assessment

If clinical suspicion of extramedullary disease (EMD) exists or the subject has a clinical history of EMD, further evaluation using imaging assessments and other diagnostics (as clinically indicated) are required for subjects at screening. Presence or absence and physical location of EMD is to be captured in the CRF.

EMD is to be assessed via physical examination, cerebrospinal fluid (CSF) assessment in case of symptoms suggestive of meningeosis leukemia, and if clinically appropriate relevant imaging techniques.

In case of EMD at baseline or (re-) appearance during the study, the lesions should be considered for confirmation by imaging or biopsy if technically and/or clinically feasible. Imaging modalities and techniques should be performed as clinically indicated and per standard of care. Selected modalities should be used consistently for a given subject, if feasible.

If clinically indicated, post baseline imaging should only be performed in these anatomical regions that demonstrate possible disease.

EMD assessment, if applicable, will be performed at screening, C2D1 and every 3 cycles thereafter thereafter until confirmed CR, and then every 6 cycles thereafter until disease progression, start of a new anti-neoplastic treatment (including HSCT), death, lost to follow-up or withdrawal of consent.

Post-treatment efficacy follow-up

Subjects who discontinue treatment for reasons other than documented disease progression/relapse from CR, start of a new anti-neoplastic treatment (including HSCT), death, lost to follow-up, or withdrawal of consent, will enter the post-treatment follow-up phase ([Section 9.1.1.2](#)). Hematology assessments must continue to be performed every 3 months, response should be assessed at least every 6 months, and bone marrow assessment should be done at least every 3 months until CR and every 6 months thereafter per [Table 8-1](#), or as clinically indicated any time in case disease progression is suspected. Further information about blood transfusions will be continuously collected throughout the post treatment follow-up period.

The post-treatment follow-up period will last until patient's documented disease progression/relapse (per ELN criteria ([Döhner et al 2017](#)), see [Table 8-2](#)), death, lost to follow-up, or withdrawal of consent or the end of study whichever comes first. Post-treatment antineoplastic therapies including HSCT will continue to be captured during survival follow-up (see [Section 9.1.1.3](#) and [Table 8-1](#)).

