 - Dosing schedule of the ramp-up period, for subjects on moderate CYP3A4 or P-gp inhibitor, was updated to reflect USPI for venetoclax
- Section 6.2.2 - Prohibited medication

- Updated to note that vaccination against COVID-19, unless these are live vaccines, is allowed during the study. However, it was clarified that SARS-CoV-2 vaccines should not be administered the same day as study treatment as recommended by the ASCO guidelines 2021 version
- Section 6.5.2 – Definitions of dose limiting toxicities (DLTs)
 - Table 6-4 - Criteria for defining dose-limiting toxicities during the safety run-in updated
 - DLT for hematologic toxicities shortened to 42 days
 - Minor edit was performed for DLT for liver toxicities
- Section 6.5.3 – Dose modifications
 - Paragraph - Dose interruption at the start of a new treatment cycle and Table 6-6 - Dose modification for venetoclax, updated to include reference to the local label for dose modifications for venetoclax,
 - Permanent discontinuation criterion for subjects experiencing prolonged cytopenias updated to indicate that - in absence of clinical benefit for the patient per investigator assessment - subjects without recovery within 42 days should be discontinued
 - Reference to ASCO Guidelines updated to 2021 version in Table 6-5 and within paragraph of dose modifications for MBG453
- Section 6.5.4.1 – Follow-up for immune related AEs
 - Reference to ASCO Guidelines updated to 2021 version
- Section 8 – Visit Schedule and Assessments
 - The allowed visit window for BMA procedures was updated to +/- 8 days from the planned visit date. Further the maximum days allowed between BMA efficacy, extramedullary disease assessment and hematology assessments of the same visits was updated to 8 days.
 - Table 8-1 – Assessment Schedule - footnote 21 was added to clarify that the Trial Feedback Questionnaire (TFQ) is not considered study data and will be received electronically outside the clinical database
- Section 8.3.1 – Efficacy assessment
 - Updated to provide clarification on how hematology assessments should be performed in the absence of count recovery at C2D1 and beyond
 - Table 8-2 – Response classification in AML at a given evaluation time (based on IWG Cheson et al 2003, ELN 2017 Döhner et al 2017)
 - CRi definition was edited to reflect accurately ELN 2017 guidelines
- Section 8.5.1.2 Trial Feedback Questionnaire (TFQ)

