6.1.5 Treatment duration

A subject may continue study treatment and follow the protocol-defined safety assessments as scheduled until:

- Disease progression (see [Table 8-2](#))
- Relapse from CR, CRi
- Unacceptable toxicity
- Initiation of a treatment cycle is delayed due to toxicities by more than 42 consecutive days (measured from the intended start date of the new cycle (i.e. measured from Day 29 of the previous cycle) in absence of clinical benefit for the patient per investigator assessment.
- Subject is scheduled to receive HSCT or intensive chemotherapy at any time during the course of the study
- Withdrawal of consent
- Physician's decision
- Pregnancy
- Lost to follow-up
- Death
- Study termination by Novartis

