## Document History – Changes compared to previous final version of SAP

Date	Time point	Reason for update	Outcome for update	Section and title impacted (Current)
15-Jun-2020	FPFV	Creation of version 1.0	N/A - First version (based on protocol incl. amendment 1 from 10-Feb-2020 and amendment 2 from 19-May-2020)	N/A
31-Oct-2024	Prior to final analysis	Creation of version 2.0	Amendment 1 (based on protocols incl. amendment 3 from 08-Apr-2021 and amendment 4 from 22-Dec-2021 and amendment 5 from 08-Dec-2022)	

• Typos corrections and clarifications

• Naming change of study drug to investigational drug, study treatment or study treatment component, as needed.

• Based on Novartis' decision to terminate the program, the team was aligned to skip primary analysis and have a single final CSR, update the wording in section 1, 1.1, 2.1 and 2.2.

• Update to align with the protocol amendment 4:

- Sections 2.2 and 2.5.1, update DLT criteria and response criteria

• Update to align with the protocol amendment 5 and simplify analysis for leaning purpose:

- Update timing for primary endpoint across the entire document: all subjects should complete at least 12 cycles of treatment or discontinued treatment earlier, as compared to 7 cycles in original protocol.

- Sections 1.2, 2.6.1 and 2.9.3: 1) to use duration of CR and duration of CR/CRi instead of the terminologies of “RFS in CR patients” and “RFS in CR/CRi patients”; 2) add CR/CRh rate, duration

Date	Time point	Reason for update	Outcome for update	Section and title impacted (Current)

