### CR analysis (safety run-in and expansion parts)

For the CR analysis, the primary endpoint is the proportion of subjects included in the FAS and assigned to MBG453 at the 800 mg Q4W dose level (in both safety run-in and expansion parts) who achieved a complete remission (CR) as per investigator assessment.

Details on the definition of response categories which are to be captured in the eCRF by the investigator were defined in Table 8-2 of the protocol that was copied into [Table 2-3](#) below.

**Table 2-3 Response classification in AML at a given evaluation time (based on IWG Cheson et al 2003, ELN 2017 Döhner et al 2017)**

Response Category	Definition 
Complete Remission	
Bone marrow:
 

< 5% blasts

no blasts with Auer rods

 
Peripheral blood:
 

neutrophils <math>\geq 1.0 \times 10^9/L</math>

platelets <math>\geq 100 \times 10^9/L</math>

no circulating blasts

 
No evidence of extramedullary disease (such as CNS or soft tissue involvement).

Complete remission with incomplete hematologic recovery (CRi)	
Bone marrow:
 

< 5% blasts

no blasts with Auer rods

 
Peripheral blood:
 

neutrophils <math>< 1.0 \times 10^9/L</math> or platelets <math>< 100 \times 10^9/L</math>

no circulating blasts

Response Category	Definition 
	No evidence of extramedullary disease (such as CNS or soft tissue involvement).
Morphologic leukemia free state (MLFS)	
Bone marrow
 
 
• < 5% blast
 
• no blasts with Auer rods
 
 
No evidence of extramedullary disease (such as CNS or soft tissue involvement)

Partial Remission (PR)	
Bone marrow:
 
 
• < 5% blasts AND presence of blasts with Auer rods
 
 
OR
 
 
• ≥ 50% decrease from baseline in blasts in bone marrow AND blast count in bone marrow is 5% to 25%
 
 
Peripheral blood:
 
 
• neutrophils ≥ 1.0 x 10^9/L
 
• platelets ≥ 100 x 10^9/L
 
• no blasts
 

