Progressive Disease (PD)	
Evidence for an increase in bone marrow blast percentage and/or increase of absolute blast counts in the blood
 
 
• >50% increase in marrow blasts from maximum remission or baseline ,whatever is lower (a minimum 15% point increase is required in cases with <30% blasts at baseline; or persistent marrow blast percentage of >70% over at least 3 mo; without at least a 100% improvement in ANC to an absolute level (>0.5 X 10^9/L [500/µL], and/or platelet count to >50 X 10^9/L [50 000/µL] nontransfused); or
 
• >50% increase in peripheral blasts (WBC X % blasts) to >25 X 10^9/L (>25 000/ µL) (in the absence of differentiation syndrome); or
 
• New extramedullary disease
 

Stable disease (SD)	Absence of CR, CRi, PR, MLFS, and criteria for PD or relapse are not met
Relapse from CR or CRi	
Only in patients with a CR or CRi . Any of the following:
 
 
• Reappearance of blasts in peripheral blood
 
 
OR
 
 
• ≥ 5% blasts in bone marrow
 
 
OR
 
 
• (Re-)appearance of extramedullary disease
 

Unknown	In case the response assessment was not done or the assessment was incomplete

The investigator does not determine best overall response, he/she is assessing only the response based on the given bone marrow and peripheral blood data, as well as on the presence or absence of extramedullary disease. The best overall response is the best disease response recorded from the start of the treatment until the first occurrence of relapse or death. Best response will be derived by Novartis for each subject as one of the following: CR, CRI, MLFS, PR, SD, PD, and unknown for all other cases.

The primary estimand related to CR rate is described by the following attributes:

1. Population: subjects with newly-diagnosed acute myeloid leukemia (AML) who are not suitable for intensive induction chemotherapy as defined by inclusion/exclusion criteria and who are assigned to the MBG453 800 mg Q4W dose level.
2. Primary variable: percentage of subjects achieving a complete remission (CR) as per investigator assessment.

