## 4. Change to protocol specified analyses

Not applicable.

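### As extracted, Protocol Table 8-2 states the peripheral-blast limit for progressive disease as both >5 x 10^9/L and >25 000/µL, a five-fold contradiction in a rule that ends treatment

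*Protocol*

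**What the plan says.** Protocol Table 8-2 defines the blood criterion for progressive disease as a >50% "increase in peripheral blasts (WBC X % blasts) to >5 X" 10^9/L, with >25 000/µL in the bracket, in the absence of differentiation syndrome. SAP section 2.5.1 describes its response categories as those "which are to be captured in the eCRF by the investigator were defined in Table 8-2 of the protocol that was copied into" Table 2-3. That table has a >50% "increase in peripheral blasts (WBC X % blasts) to >25 X" 10^9/L, with the same bracket of >25 000/µL.

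The rule is operative. Under Protocol 8.3.1 the investigator assesses response locally against Table 8-2. When data are incomplete, progression in a single compartment, blood included, is enough to avoid a response of unknown. Protocol 6.1.5 states: "A subject may continue study treatment and follow the protocol-defined safety assessments as scheduled until" one of a list of events occurs. Disease progression, with a pointer to Table 8-2, is first on that list. Section 6.1.5.1 rules out treatment after progression. Documented progression also ends post-treatment efficacy follow-up (8.3.1).

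**The concern.** A response criterion should give one threshold. Here a site could read 5 or 25 x 10^9/L from the same line. A site that took 5 would call progression at a fifth of the blast count implied by the bracket. It would then stop all study treatment and cease efficacy assessments in a subject who, at 25, might still be in stable disease. The doubtful figure is in the protocol, which is the document that sites apply. A correct figure in the SAP does not undo a call already made, because the SAP takes investigator-assessed responses as recorded.

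**Working it through.** **Inputs.** Protocol Table 8-2, Progressive Disease row: ANC 0.5 x 10^9/L with 500/µL; platelets 50 x 10^9/L with 50 000/µL; blasts 5 x 10^9/L with 25 000/µL. SAP Table 2-3: blasts 25 x 10^9/L with 25 000/µL.

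**Step 1: unit conversion.** One litre is 10^6 µL, so x times 10^9/L equals x times 1 000/µL.

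| Item | Printed per litre | Converted | Printed per µL | Agree? |
|---|---|---|---|---|
| ANC (protocol) | 0.5 x 10^9/L | 500/µL | 500 | yes |
| Platelets (protocol) | 50 x 10^9/L | 50 000/µL | 50 000 | yes |
| Blasts (protocol) | 5 x 10^9/L | 5 000/µL | 25 000 | no |
| Blasts (SAP) | 25 x 10^9/L | 25 000/µL | 25 000 | yes |

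The ratio for the mismatched pair is 25 000 / 5 000 = 5. The other two pairs in the cell are right, so the fault is confined to one figure.

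**Step 2: which counts are classified differently.** Let b be the reference blast count and c the new count, both in 10^9/L. Progression needs c > max(1.5b, 5) under one limit and c > max(1.5b, 25) under the other. While 1.5b is below 25, the calls differ for max(1.5b, 5) < c ≤ 25.

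| Reference b | Calls differ for c |
|---|---|
| up to 3.33 | above 5, up to 25 |
| 4 | above 6, up to 25 |
| 8 | above 12, up to 25 |
| 12 | above 18, up to 25 |
| 16.7 or more | no difference |

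For example, WBC 20 with 60% blasts gives 20 x 0.60 = 12. With a >50% rise, that is progression at 5 but not at 25. WBC 40 with 70% blasts gives 28, which is progression under both. Inclusion criterion 10 requires WBC below 25 x 10^9/L, so reference counts in the affected range are plausible at entry.

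**Step 3: what each endpoint uses.**
- *CR, OS, CR/CRh.* The definitions do not use this limit. The ELN 2022 derivation in SAP 5.2.2 lists no progression category.
- *Duration of CR and of CR/CRi.* Once a subject is in CR or CRi, any reappearance of blasts in blood is already relapse under Table 8-2, so the limit adds essentially nothing.
- *Best overall response.* SAP 2.5.1 takes the best response up to relapse or death. A progression call matters only where no stable disease or better was recorded at another assessment, for example when C2D1 was the progression call. The result appears in the by-subject listing of SAP 2.5.4.
- *EFS.* Progression outside CR is not itself an event. Protocol 12.5.1, however, counts earlier permanent discontinuation as treatment failure, set to Day 1, so a mistaken stop could enter EFS indirectly.
- *Design figures.* Success at 49 or more of 80 gives a type I error of 0.0283 at a true rate of 50% and power of 0.7951 at 65%. These match the stated 2.8% and 79.5%, and neither depends on the progression limit.

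**The case against.** The strongest reply is that a digit may have been lost in reading the PDF. The bracket in the same line and the SAP table both point to 25, so the printed page may well read 25. That is possible but not shown. It is the reason to look at the page before doing anything else. It is also fair to say that a reader of the line sees 25 000/µL beside the 5, and that the protocol names the published IWG and ELN criteria behind the table. Nothing in the documents shows that any site applied 5.

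A reader might go further and infer that the SAP silently changed a protocol criterion. The SAP history for section 2.5.1 says only "update DLT criteria and response criteria" to align with Amendment 4, and for Table 8-2 the Amendment 4 log records only that the "CRi definition was edited to reflect accurately ELN 2017 guidelines". SAP section 4, "Change to protocol specified analyses", is marked not applicable. The documents do not support that inference. The SAP history lists changes from the previous SAP version, which is not available and may already have printed 25. If the figure did change, the entry "Typos corrections and clarifications" could cover it. The amendment log records changes between protocol versions. Section 4 concerns analyses, whereas this is a criterion that investigators apply when recording response.

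A reader might also infer that the primary result is compromised. It is not: CR is defined without this limit. A mistaken early stop could in principle cost a subject a later CR, but that route is indirect and cannot be sized from the documents.

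**Conclusion.** The contradiction stands on the text as extracted: two limits five-fold apart in one line of the rule used to call progression and stop treatment. Its reach is small. It is confined to progression versus stable-disease calls, treatment stops and best overall response in subjects not in CR or CRi, with a possible indirect effect on EFS through early discontinuation. The number of subjects affected is unknown and may be zero. The conclusion assumes that the page prints what was extracted and that 25 was intended; the bracket and the SAP table both support the latter. If the page prints 25, the point falls away entirely. Severity is minor.

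**What to change.** 1. Check the source page of Protocol Table 8-2. If it reads 25, stop there.
2. If it reads 5, correct it to >25 x 10^9/L (>25 000/µL) and tell sites. Enrolment was complete by Amendment 5 and the termination letter went out on 11-Jan-2024, so this will change little in conduct; the data check matters more.
3. Before database lock, list progression calls made on the blood criterion alone with blasts above 5 and up to 25 x 10^9/L, and ask the investigator to confirm or revise each one. Only the investigator should change a call, since the response endpoints concerned rest on investigator assessment.
4. Report any affected treatment stops in the CSR. If the database is already locked, a CSR note is enough.

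The cost is one corrected figure, a notice to sites and a short listing with queries. No new assessments are needed and no planned analysis changes.
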